3.1.2 Follow-Up Period (12 Months FOLLOWING REPORT)

Subjects enrolled in the study will concurrently undergo WGS as part of their clinical care, with samples sent to the Illumina Clinical Services Laboratory (ICSL) for clinically-validated testing.

3.1.3 Early Termination and Withdrawal

Subjects may withdraw from the study at any time and for any reason. This would result in removal of any identifying information from recorded databases.

3.2 Study Duration, Enrollment and Number of Sites

3.2.1 Duration of Study Participation

Study participation will last for 12 months following the disclosure of results.

3.2.2 Total Number of Study Sites/Total Number of Subjects Projected

This is a single-site study located at the Children's Hospital of Philadelphia (CHOP). Study recruitment will continue until 100 trios (or duos) have been enrolled.

3.3 Prospective Study Population (WGS Cohort)

3.3.1 Inclusion Criteria & Initial Candidate Assessment

These criteria have been selected in order to ensure that selected cases fit the definition of a leukodystrophy³³ and allow accurate calculations of diagnostic efficacy based on time to diagnosis from initial identification of a white matter disorder. The heritable leukodystrophies affect males and females equally, with the exception of Pelizaeus Merzbacher and ALD, which are X-linked. We expect therefore that males and females will be equally represented in the population of patients with unclassified leukodystrophies. The age of presentation is variable, ranging from infancy to adulthood. All ethnicities are equally represented in these disorders, and we expect ethnicities to be represented based on U.S. census data of population distribution.

3.3.2 Inclusion Criteria – All Candidates

- 1) Abnormalities of the white matter signal on neuroimaging (MRI) with T2 hyperintensity which must be diffuse or involve specific anatomical tracts consistent with a genetic diagnosis;
- 2) No pre-existing genetic diagnosis;
- 3) A clinical decision has been made to perform WGS;
- 4) Less than 18 years of age (exception for affected sibling of the proband);
- 5) Availability of both biologic parents for blood sampling;
- 6) Availability of both biological parents to provide informed consent;
- 7) Concurrently enrolled in CHOP IRB 14-011236 (Myelin Disorders Biorepository Project)

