To address these issues, the study team conducted an investigation of patients with suspected leukodystrophies or other genetic disorders affecting the white matter of the brain at the time of initial confirmation of MRI abnormalities, with prospective collection of patients randomly received on a “first come, first served” basis from a network of expert

clinical sites. Subjects were randomized to receive early (1 month) or late (6 months) WGS, with Standard of Care (SoC) clinical analyses conducted alongside WGS testing. An interim analysis performed in May 2018 assessed these study outcomes for a cohort of thirty-four (34) enrolled subjects. Two of these subjects were resolved before complete enrollment and were retained as controls. Nine subjects were stratified to the Immediate Arm, of which 5 (55.6%) were resolved by WGS and 4 (44.4%) were persistently unresolved. Of the 23 subjects randomized to the Delayed Arm, 14 (60.9%) were resolved by WGS and 5 (21.7%) by SoC, while the remaining 4 (17.4%) remained undiagnosed. The diagnostic efficacy of WGS in both arms was significant relative to SoC ($p<0.005$). The time to diagnosis was significantly shorter in the immediate WGS group ($p<0.05$). The overall diagnostic efficacy of the combination of WGS and SoC approaches was 26/34 (76.5%; 95% CI = 58.8% to 89.3%) over <4 months, greater than historical norms of <50% over more than 5 years.

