3.3.3 Exclusion Criteria – All Candidates

- 1) Candidates with acquired disorders, including infection, acute disseminated encephalomyelitis (ADEM), multiple sclerosis, vasculitis or toxic leukoencephalopathies;
- 2) Patients who have had previous next-generation genetic sequencing*, including WES or WGS;
- 3) Those with no third-party payer insurance, unable to receive standard of care diagnosis and therapeutic approaches;

- 4) Candidates who have already received a diagnosis.

***Note:** Karyotype or microarray testing that did not yield a definitive diagnosis should not be considered as an excluding factor.

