5 STATISTICAL CONSIDERATIONS

5.1 Analysis Plan and Sample Size Determination

5.1.1 Analysis for Aim 1

The proportion of subjects who have a change in diagnosis status and the conditional proportion of subjects who were impacted by WGS will be calculated for the cohort, with 95% confidence intervals (95% CI). Individuals who were recruited to the previous (randomized crossover) version of this protocol will be included.

5.1.2 Analysis for Aim 2

The frequency and conditional proportion of subjects who received downstream changes in clinical management after a diagnostic result through WGS will be calculated for the cohort, with 95% confidence intervals (95% CI). The type of downstream clinical changes will be reported. Individuals who were recruited to the

previous (randomized crossover) version of this protocol and received a diagnosis through WGS will be included.

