5.1.3 Sample Size Determination

5.1.3.1 Aim 1: *Due to the rapid changes in standard of care, many of the control arm were ineligible for participation as a historical control, since they received WGS through clinical care. These changes to standard of care also hindered study enrollment sample size goals. The total sample size that was achieved is N=80 (including the subjects enrolled in the randomized control arm). Power calculations are no longer needed for comparison to control arm.*

5.1.3.2 Aim 2 Refer to 5.1.2.

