8 PUBLICATION

As this study may involve findings of novel genes implicated in disease, identification of a specific individual from the diagnosis could be discerned in publications or presentations although this is unlikely in a cohort of 100 participants and their biological parents. It is doubtful that any demographic information could identify an individual.

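### Do eligible affected siblings make the planned 95% confidence intervals too narrow?

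*Combined protocol and SAP*

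**What the plan says.** Section 3.3.2 limits age with one exemption: "Less than 18 years of age (exception for affected sibling of the proband". No inclusion or exclusion criterion restricts a family to one child. Section 3.3.3 excludes anyone with earlier next-generation sequencing and also "Candidates who have already received a diagnosis".

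The unit of analysis is the subject. For Aim 1, section 5.1.1 reports those who "were impacted by WGS will be calculated for the cohort, with 95% confidence intervals (95% CI"). For Aim 2, section 5.1.2 reports management changes "after a diagnostic result through WGS will be calculated for the cohort, with 95% confidence intervals (95% CI"). Neither section names an interval method or a rule for related subjects.

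The counts are expressed in different ways:

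- Section 3.2.2: "Study recruitment will continue until 100 trios (or duos) have been enrolled".
- Section 5.1.3: "The total sample size that was achieved is N=80", with no count of families.
- Section 8 says that recognition of an individual is "unlikely in a cohort of 100 participants and their biological parents".

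The only interval printed anywhere is the interim result in section 1.1: "26/34 (76.5%; 95% CI = 58.8% to 89.3"%).

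**The concern.** The Aim 1 outcome is whether sequencing changes diagnostic status. Two affected siblings who carry the same variant will tend to be diagnosed together or missed together, so a pair carries less information than two unrelated children. A binomial interval that counts them as independent then understates the uncertainty.

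Proportions with 95% intervals are the only inference planned for either aim, and section 5.1.3 drops the power calculation. If the intervals were materially too narrow, the study's whole statement of precision would be off. The age exemption for siblings also shows that their entry was foreseen, which makes the silence in section 5.1 look like an oversight. The per-subject estimate itself is not in question.

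**Working it through.** **Inputs.** N=80 (section 5.1.3). The yield of sequencing alone in the interim data (section 1.1) is (5+14)/(9+23) = 19/32 = 0.594. The yield of sequencing plus standard of care is 26/34 = 0.765. Assumed, because the documents are silent: the number of sibling pairs k, the within-pair correlation ρ, and about 48 diagnosed subjects for Aim 2 (80 × 0.594 = 47.5).

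**1. The plan's own interval.** Clopper-Pearson for 26/34 takes the 2.5% point of Beta(26, 9) and the 97.5% point of Beta(27, 8). The result is 58.8% to 89.3%, exactly as printed. Wilson gives 60.0% to 87.6% and does not match. The sponsor's working method is therefore an exact interval.

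**2. Loss of information.** With k pairs among N subjects,

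Var(p̂) = [p(1−p)/N] × (1 + 2kρ/N).

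At N=80, p=0.594 and ρ=1, the normal-theory half-width without pairs is 1.96 × √(0.594 × 0.406/80) = 10.76 points.

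- k=4: factor 1 + 8/80 = 1.10; half-width 10.76 × √1.10 = 11.29 points.
- k=8: factor 1 + 16/80 = 1.20; half-width 10.76 × √1.20 = 11.79 points.

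**3. Actual coverage of the unadjusted Clopper-Pearson interval.** This is an exact enumeration of N−2k independent subjects plus k pairs, with P(both) = p² + ρp(1−p) and P(neither) = (1−p)² + ρp(1−p). For Aim 1 at N=80 and ρ=1:

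| k | p=0.594 | p=0.765 | average, p 0.55–0.80 |
|---|---|---|---|
| 0 | 96.0% | 95.3% | 96.2% |
| 1 | 95.8% | 95.0% | 96.0% |
| 2 | 95.5% | 94.8% | 95.8% |
| 4 | 95.0% | 94.2% | 95.3% |
| 8 | 93.9% | 93.0% | 94.2% |

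Halving ρ to 0.5 has the effect of halving k, so 8 half-correlated pairs still average 95.3%.

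**4. Aim 2.** Only diagnosed pairs enter this denominator. Of 8 enrolled, fully concordant pairs at a yield of 0.594, the expected number is 8 × 0.594 = 4.75. The paired share is then 9.5/48 = 20%, the same as 16/80 in Aim 1. Taking the number of diagnosed pairs as Binomial(8, 0.594), and ρ=1 for the management outcome as well, average coverage over p from 0.40 to 0.90 is 94.7%. With 4 enrolled pairs it is 95.7%. Placing all 8 pairs among the 48 would give 93.4%, but that requires all 16 siblings to be diagnosed against 32 of the other 64 subjects.

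**5. Worked example.** Suppose 48/80 are diagnosed and there are 4 pairs, three with both diagnosed and one with neither. The other 72 subjects are 42 diagnosed and 30 not. The sum of squared family residuals is

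3(0.8)² + 1(1.2)² + 42(0.4)² + 30(0.6)² = 1.92 + 1.44 + 6.72 + 10.80 = 20.88.

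The clustered variance over 76 families is (76/75) × 20.88/80² = 0.003306, against 0.6 × 0.4/80 = 0.003. The design effect is 1.102 and the effective N is 80/1.102 = 72.6. Clopper-Pearson moves from 48.4%–70.8% to 47.8%–71.3%.

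**6. What an adjustment would gain.** Clopper-Pearson on the effective N averages about 96.3% at N=80, where the unadjusted interval with 4 pairs averages 95.3%. When pairs are few, the adjustment adds conservatism to an interval that is already adequate on average.

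**The case for a change.** The strongest case for a change runs as follows. The exclusions narrow the sibling route but do not close it, since two undiagnosed siblings sequenced together both qualify. The section 8 wording is a privacy remark, not an enrolment rule. The plan names no interval method, so nothing commits the analyst to the exact one. With Wilson, average coverage over p from 0.40 to 0.80 is 95.0% with no pairs, 94.5% with 2 and 93.6% with 5. Even the exact interval dips below 95% at single values of p, for example 94.2% at p=0.765 with 4 concordant pairs. A family identifier and one sentence would cost little.

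Most of this is true, and the gap in the text is real. It does not amount to a needed change. The dips are about one percentage point and rest on complete concordance. For Aim 2 that is a strong assumption, because a shared variant does not make two children's management records change together. Larger losses need many pairs: the exact interval averages 93.6% with 10 pairs and 90.9% with 20 (p from 0.40 to 0.80). Twenty pairs would make 40 of the 80 subjects siblings of one another, which is hard to square with recruitment counted in trios or duos. Which adjusted interval is best is open to debate, so prescribing one would settle a matter of preference for a condition not shown to arise. What stands is that readers would be helped by the number of families beside N, which is ordinary reporting.

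**Conclusion.** The concern does not call for a change to the plan. Section 5.1 is silent on multi-child families, but no pair is documented and the texts on recruitment and publication read most naturally as one child per set of parents. If a few pairs were enrolled, the exact interval that the sponsor has used before keeps average Aim 1 coverage at or above 95% up to about 4 fully concordant pairs, and at 94.2% with 8. Aim 2 fares no worse on average (94.7% with 8 enrolled pairs). In the 4-pair example the limits shift by 0.6 and 0.5 points on an interval more than 22 points wide, in a descriptive study with no hypothesis test.

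This rests on assumed pair counts, on ρ between 0.5 and 1, on about 48 diagnosed subjects, and on the same interval method being used again. It would need another look only if the data showed many more than 8 concordant pairs, and an analyst would see that on tabulating families.

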3.3.3 Exclusion Criteria – All Candidates

- 1) Candidates with acquired disorders, including infection, acute disseminated encephalomyelitis (ADEM), multiple sclerosis, vasculitis or toxic leukoencephalopathies;
- 2) Patients who have had previous next-generation genetic sequencing*, including WES or WGS;
- 3) Those with no third-party payer insurance, unable to receive standard of care diagnosis and therapeutic approaches;

- 4) Candidates who have already received a diagnosis.

***Note:** Karyotype or microarray testing that did not yield a definitive diagnosis should not be considered as an excluding factor.

3.3.4 Inclusion Criteria - Parents

- 1) Males or females 18 years or older;
- 2) Child with a suspected leukodystrophy or other suspected genetic disorder affecting the white matter of the brain.

3.3.5 Exclusion Criteria - Parents

- 1) Inability to provide consent;
- 2) Pregnant women and fetuses will not be included in this study.

Candidates who do not meet all of the enrollment criteria may not be enrolled. Violations of these criteria will be reported in accordance with IRB Policies and Procedures.

4 STUDY EVALUATIONS AND MEASUREMENTS

4.1 Study Outcome Measures

4.1.1 Prospective Collection of Clinical Utility Data

Clinical utility outcomes will be assessed using a combination of medical record review 1 year prior to (retrospective) and 1 year following (prospective) disclosure of results. An appropriately trained member of the study team will review this data for documented changes in care and clinical state, included changes in medical morbidities, surgeries, pharmacologic management of complications and implementation of disease specific therapies. The following data elements will be abstracted from patient medical records for analysis.

- Diagnostic status (primary): Results were diagnostic, non-diagnostic (negative or variant of unknown significance (VUS) with inconsistent phenotype), uncertain (previously and/or not previously reported VUS identified and requires follow-up).
- Implications of WGS: confirmed a diagnosis within the differential diagnosis prior to testing, established a new diagnosis that was not previously suspected, produced a diagnosis unrelated to the clinical indication for testing [includes incidental findings and/or secondary findings], ruled out a suspected diagnosis/ diagnoses, eliminated the need for additional tests or evaluations, contributed to the overall diagnostic evaluation of this patient.
 - Diagnostic changes in management if diagnostic result (secondary): Referrals to New Healthcare Providers (inc. Specialty)
 - Disease-specific treatment or medication Changes (inc. Type and Detail)
 - Disease-specific screening (implemented new screening, screening implemented for suspected dx was justified)
 - Decisions on palliative care

- Participation in research study (Type)
- Family planning, counseling, or support (Type)

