3.1.1 Screening Procedures

Candidates with a suspected leukodystrophy or other suspected genetic disorder affecting the white matter of the brain will be provided with information about the study by a qualified member of the study team. Interested candidates will be invited to enroll in CHOP IRB 14-011236 to facilitate collection and review of medical records. At a minimum, these records must include a copy of the most recent neurologic exam and brain MRI. Additional notes, reports, test results, imaging studies, etc. will be requested if available.

Candidates who meet basic eligibility requirements will then be independently reviewed by [name], MD, a pediatric neurologist at McGill University with significant expertise in MRI pattern recognition. [name] may receive abstract clinical summaries, as well as radiology studies that have been coded with a unique study identifier generated by the CHOP study team. [name] will not be able to link these study identifiers to PHI.

MRIs will be analyzed according to a publicly available non-computational algorithm accessible to even non-expert child neurologists and geneticists⁴⁶. Candidates may be enrolled irrespective of the clinician's presumptive diagnosis (even if the clinician feels there is an unambiguous diagnosis based on MRI and initial clinical assessment), as long as no confirmatory testing has been performed. Each candidate's MRIs must be reviewed by at least two of the four experts. If necessary, candidates will be reclassified with respect to their pre-test diagnostic probabilities.

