7.3.5 Potential Benefits

Study participation is not intended to confer any direct benefit to subjects. The investigators are confident that the knowledge gleaned from this study will support wider implementation and access to whole genome sequencing.

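### Section 4.1.1 does not fix the pre-test differential or baseline care before the abstractor knows the WGS result, so hindsight can affect the Aim 2 proportion

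*Combined protocol and SAP*

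**What the plan says.** Section 4.1.1 assesses clinical utility by "medical record review 1 year prior to (retrospective) and 1 year following (prospective) disclosure of results". On who does this, it says: "An appropriately trained member of the study team will review this data for documented changes in care and clinical state". It continues: "The following data elements will be abstracted from patient medical records for analysis".

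Three of the listed elements matter here:

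- The implications of WGS include whether the result "confirmed a diagnosis within the differential diagnosis prior to testing, established a new diagnosis that was not previously suspected".
- The Aim 2 block is headed "Diagnostic changes in management if diagnostic result (secondary", so its items are recorded only for children with a diagnostic result.
- The screening item in that block includes the option "screening implemented for suspected dx was justified".

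Section 4.1.2 accepts a change that is documented, and also one inferred from the providers seen or the interventions recommended. Section 2.2 requires the change to be significant and directly due to the WGS diagnosis, but no rule is given for judging either.

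Neither section 4.1 nor section 5 mentions masking, an order of abstraction, a locked baseline, a second abstractor or adjudication. Section 5.1.2 plans a frequency and a conditional proportion with a 95% CI. Section 5.1.3.1 drops the comparison with a control arm.

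**The concern.** Two readings of the baseline year feed the results: which disorders were in the differential before testing, and what care was already in place. Both call for interpretation. A broad pre-test note may or may not be taken to include the disorder later found. An earlier follow-up visit may or may not be taken as the screening later credited to WGS. A reader who knows the result can settle such doubts in its light.

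Aim 2 is the more exposed. Its items are conditional on a diagnostic result, so the result is known before change is recorded, and no baseline form has to be completed first. The justified-screening option goes further: on its natural reading, care begun before the result enters the list of changes because the result supported it. With no comparator, such errors cannot cancel between arms, and the planned interval reflects sampling error only.

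**Working it through.** The plan states no misclassification rate and no expected Aim 2 proportion, so there is no figure of its own to reproduce on this point. The calculation below shows scale under stated assumptions. It does not estimate the actual bias.

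**Inputs from the documents**
- Interim WGS diagnoses (section 1.1): 5 of 9 in the Immediate Arm and 14 of 23 in the Delayed Arm, so 5 + 14 = 19.
- Interim cohort (section 1.1): 34 subjects, or 32 without the two retained as controls.
- Achieved sample (section 5.1.3.1): N=80.

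The one interval given in section 1.1 reproduces: 26/34 = 76.5%, exact (Clopper-Pearson) 95% CI 58.8% to 89.3%. The same method is used below.

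**Aim 2 denominator (assumption: the interim yield holds in all 80)**
- 80 × 19/34 = 44.7
- 80 × 19/32 = 47.5

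This gives about 45 to 48 children.

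**Upward error.** Let p be the true proportion changed and f the share of true non-changers counted as changed. Then observed = p + (1 − p)f, and the shift is (1 − p)f. Coverage is the chance that the nominal 95% CI contains p, with 45 children.

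| True p | CI half-width, 45 children (points) | Shift, f=10% | Shift, f=20% | Coverage, f=10% | Coverage, f=20% |
|---|---|---|---|---|---|
| 30% | 14.2 | 7 | 14 | 88% | 59% |
| 50% | 15.3 | 5 | 10 | 92% | 78% |
| 70% | 14.2 | 3 | 6 | 94% | 88% |

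With 48 children the half-widths are 13.6, 14.8 and 13.6 points. For a shift as large as the half-width with 45 children, f would have to be 14.2/70 = 20%, 15.3/50 = 31% and 14.2/30 = 47% respectively.

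**Downward error.** If instead a share g of true changers is judged to have had the care already, the shift is −pg. At g = 10% to 20% this runs from −0.30 × 0.10 = −3 points to −0.70 × 0.20 = −14 points. The documents do not say which direction prevails.

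**Results already known.** Section 5.1 includes subjects recruited under the randomized version, and 34 had outcomes assessed in May 2018 (section 1.1). If all 34 are among the 80 (assumption), the team knew the results of 34/80 = 42.5% by then.

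**The case against.** The case on the other side has several parts.

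- **Pre-test information exists.** Section 3.1.1 provides for independent review at screening, MRI reading by at least two of four experts, and reclassification by pre-test diagnostic probability. The baseline notes also predate the result. This stands, and it gives a usable anchor for the differential. But section 4.1.1 does not tie the confirmed-versus-new split to it, and section 3.1.1 does not describe a record of baseline care, so Aim 2 gains little protection.
- **Hindsight is possible, not shown.** In section 4.1.1, retrospective describes the window of records. The date of abstraction is not given, and the text does not say that one person reads both years together. This stands: the documents support only that hindsight can enter.
- **The split is descriptive.** Section 5 does not name it as an analysis; section 5.1.1 refers only to subjects affected by WGS. This stands, and so the split comes second here.

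A reader might also infer more than the documents support:

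- That the study masks its MRI review and leaves only the outcome review open. The external reviewer "will not be able to link these study identifiers to PHI", but that is a confidentiality measure at screening, not masking to an outcome.
- That the team is disposed towards a favourable reading, because section 7.3.5 says: "The investigators are confident that the knowledge gleaned from this study will support wider implementation". That sentence concerns potential benefits and says nothing about abstraction.
- That the primary outcome is compromised. Diagnostic status classifies the WGS result itself and does not depend on reading the baseline year.

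**Conclusion.** The gap is real and worth closing. Nothing in section 4.1.1 fixes the pre-test differential or baseline care before the result is known, and the Aim 2 items are conditional on that result. Hindsight can affect the Aim 2 numerator and, secondarily, the descriptive confirmed-versus-new split. Primary diagnostic status is outside the point.

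Size and direction cannot be determined from the documents. Under the assumed denominator, upward errors of 10% to 20% among true non-changers give about 3 to 14 points, smaller than or at most similar to the half-width of the interval. A reader might infer that the bias exceeds the sampling uncertainty. That would need error rates from about 20% (true proportion 30%) to 47% (true proportion 70%), for which the documents give no basis.

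**What to change.** Amend section 4.1.1, using existing staff and REDCap:

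1. From notes dated before disclosure only, record the named differential, anchored to the section 3.1.1 pre-test assessment, and the baseline status of every listed Aim 2 item, including research participation and family planning or counseling. Lock this form before the WGS report and later notes are opened.
2. Then abstract the year after disclosure. Count a change only if it differs from the locked baseline and the record attributes it to the WGS diagnosis. A purely mechanical before-and-after comparison would not do: these are degenerative disorders, so changes due to progression would be credited to WGS and the causal requirement of section 2.2 would be lost.
3. Report Aim 2 with and without two groups: the justified-screening option, which by its nature need not differ from baseline, and changes only inferred from providers seen or interventions recommended.
4. For children already abstracted, rebuild the baseline from dated notes, by a team member not involved in disclosure where possible. Report how many classifications change, and state that masking is incomplete where the team knows the result.

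The cost is a modest amount of staff time, mostly for re-abstraction. No additional procedure or patient contact is needed.
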